3 SAMPLE SIZE

Phase 1 Dose Escalation:

The sample size of approximately 24, including 12 from monotherapy and 12 from combination therapy, is not based on a statistical power calculation. The number of participants enrolled will be dependent on the DLT incidence. The estimated number of participants should provide adequate information for the dose escalation and safety objectives of the study.

Phase 2 Dose Expansion:

It is estimated that up to approximately 361 participants may be enrolled in the monotherapy and combination therapy arms (approximately 129 participants for monotherapy and 232 participants for combination therapy). The iORR is monitored using the BOP2 design. For each indication, with assumptions mentioned in the Statistical Hypotheses below, the statistical power would be approximately 0.80 while controlling the type I error rate at 0.05 (1-sided).

Monotherapy

Statistical Hypotheses:

H0: iORR is 10%, under which the treatment is deemed as unacceptable.

H1: iORR is at least 25%, under which the treatment is deemed as acceptable.

Combination Therapy

Statistical Hypotheses:

Metastatic Melanoma CPI Naïve

H0: iORR is 25%, under which the treatment is deemed as unacceptable.

H1: iORR is at least 40%, under which the treatment is deemed as acceptable.

Metastatic Melanoma CPI Refractory

H0: iORR is 13%, under which the treatment is deemed as unacceptable.

H1: iORR is at least 28%, under which the treatment is deemed as acceptable.

Ovarian Cancer

H0: iORR is 15%, under which the treatment is deemed as unacceptable.

H1: iORR is at least 30%, under which the treatment is deemed as acceptable.

Colorectal Cancer

H0: iORR is 18%, under which the treatment is deemed as unacceptable.

H1: iORR is at least 33%, under which the treatment is deemed as acceptable.

4 ANALYSIS SETS

In accordance with International Conference on Harmonization (ICH) recommendations in guidelines [E3](#) and [E9](#), the following analysis sets will be used for the analyses. Full Analysis Set (FAS) and Response Analysis Set (RAS) will be used for efficacy analysis. Safety Analysis Set (SAF) will be used for the analyses of safety variables. Pharmacokinetic Analysis Set (PKAS) will be used for pharmacokinetic analyses. The biomarker pharmacodynamics analysis set (PDAS) will be used for all analyses of pharmacodynamics data. The data from all participants who were enrolled in the study will be included in the data listings. All enrolled participants are those who signed the informed consent form and were assigned a subject number.

For each dose level group, the number and percentage of participants will be characterized for all treated participants and by each analysis set.

Population	Description
Enrolled	All participants who sign the informed consent form are allocated to treatment.
Full Analysis Set (FAS)	All participants who are enrolled and receive at least one dose of study treatment.
Response Analysis Set (RAS)	The response analysis set will consist of all participants who are enrolled and receive at least 1 dose of IP and have at least 1 post baseline primary efficacy measurement.
Safety Analysis Set (SAF)	All participants who take at least 1 dose of IP.

Pharmacokinetic Analysis Set (PKAS)	The PKAS consists of the administered population for which pharmacokinetics data are available for at least 1 time point. Additional participants may be excluded from the PKAS at the discretion of the pharmacokineticist.
Pharmacodynamic Analysis Set (PDAS)	The PDAS will include the participants from the administered population for whom sufficient pharmacodynamic measurements were collected. The PDAS will be used for all analyses of pharmacodynamic data.
DLT Evaluation Analysis Set (DEAS)	The DEAS is defined as all participants in SAF excluding participants who meet any of the following criteria: 
• Participant is discovered to have enrolled without fully satisfying eligibility criteria.• Participant received less than the planned dose in cycle 1 for reasons other than DLT.• Participant has no DLT and withdraws from the study before the end of DLT evaluation period. The DEAS will be used for the analysis of DLT data.

5 ENDPOINTS

5.1 Efficacy Endpoints

Tumor-related efficacy variables are evaluated by the Response Evaluation Criteria in Solid Tumors (RECIST) 1.1 and guidelines for response criteria for use in trials testing immunotherapeutics (iRECIST) ([Seymour, L., et al., 2017](#)).

5.1.1 Primary Efficacy Endpoints

Due to study's early closure, independent central review data will not be collected; investigator assessed endpoints will be presented.

5.1.1.1 Objective Response Rate per iRECIST (iORR)

iORR is defined as the proportion of participants for each dose level whose best overall response is rated as confirmed iCR or iPR per iRECIST. Endpoints will include:

- iORR with confirmed response by investigator assessment
- iORR with unconfirmed response by investigator assessment

5.1.2 Secondary Efficacy Endpoints

5.1.2.1 Objective Response Rate per RECIST (ORR)

ORR is defined as the proportion of participants for each dose level whose best overall response is rated as CR or PR per RECIST v1.1 for the endpoints of:

- ORR with confirmed response by investigator assessment
- ORR with unconfirmed response by investigator assessment

5.1.2.2 Disease Control Rate per iRECIST (iDCR)

iDCR is defined as the proportion of participants for each dose level whose best overall response is rated as confirmed iCR, iPR or stable disease (iSD) per iRECIST.

5.1.2.3 Disease Control Rate per RECIST v1.1 (DCR)

DCR is defined as the proportion of participants for each dose level whose best overall response is rated as confirmed CR, PR or SD per RECIST v1.1.

5.1.2.4 Overall Survival (OS)

OS is defined as the time from the date of first dose until the date of death from any cause (death date – first dose date + 1). For a participant who is not known to have died by the end of study follow-up, OS is censored at the date of last contact (date of last contact – first dose date + 1).

Table 1 OS Definition

Situation	Date of Event or Censor	Outcome
Death before or on analysis cutoff date	Date of death	Event
Death after analysis cutoff date	Analysis cutoff date	Censor
Last known alive is before or on cutoff date	Last known alive date	Censor
Last known alive is after cutoff date	Analysis cutoff date	Censor

OS = Date of Event or Censor – Date of First Dose +1

5.1.2.5 Progression-free Survival per iRECIST (iPFS)

iPFS is defined as the time from the start of the study treatment until death from any cause or radiographic disease progression assessed per iRECIST by investigator assessment, whichever occurs first.

If iUPD occurs but iSD, iPR, or iCR is observed any time subsequent to iUPD, iUPD status will be disregarded for determination of iPFS.

Table 2 iPFS Definition

iPFS		
Situation	Date of Event or Censor	Outcome
No evaluable post-baseline imaging assessments, no death	Date of first dose (Day 1)	Censor
Participant did not receive new anti-cancer therapy:		
iCPD	First date where iUPD criteria are met	Event
No iCPD, but death recorded on eCRF	Date of death	Event
No iCPD nor death and not in one of the following cases :a)if the participant stops protocol treatment because they were not judged to be clinically stable, b) no further response assessments are done (because of participant refusal, protocol non-compliance, or participant death); c) the	Date of last radiological assessment	Censor

iPFS		
Situation	Date of Event or Censor	Outcome
next timepoint responses are all iUPD, and iCPD never occurs;		
No iCPD nor death and is in one of the following cases : a)if the participant stops protocol treatment because they were not judged to be clinically stable, b) no further response assessments are done (because of participant refusal, protocol non-compliance, or participant death); c) the next timepoint responses are all iUPD, and iCPD never occurs;	First date where iUPD criteria are met	Event
Participant received new anti-cancer (ACT) therapy:		
No progression before new ACT	Date of last radiological assessment before start of new anti-cancer therapy	Censor
iCPD before new ACT	First date where iUPD criteria are met	Event
iUPD before new ACT and not in one of the following cases : a)if the participant stops protocol treatment because they were not judged to be clinically stable, b) no further response assessments are done (because of participant refusal, protocol non-compliance, or participant death); c) the next timepoint responses are all iUPD, and iCPD never occurs;	Date of last radiological assessment before start of new anti-cancer therapy	Censor
iUPD before new ACT and is in one of the following cases : a)if the participant stops protocol treatment because they were not judged to be clinically stable, b) no further response assessments are done (because of participant refusal, protocol non-compliance, or participant death); c) the next timepoint responses are all iUPD, and iCPD never occurs;	First date where iUPD criteria are met	Event
Missed ≥ 2 scheduled radiological assessments		
If last assessment prior to missing ≥ 2 scans is iUPD	First date where iUPD criteria are met	Event
If last assessment prior to missing ≥ 2 scans is not iUPD and no progression or death after missing ≥ 2 scans	Date of last radiological assessment	Censor

iPFS		
Situation	Date of Event or Censor	Outcome
No post-baseline tumor imaging prior to missing 2 scans and progression or death after missing ≥ 2 scans	Date of first dose (Day 1)	Censor
No post-baseline tumor imaging prior to missing 2 scans and no progression or death after missing ≥ 2 scans	Date of last radiological assessment	Censor
If radiographical progression or death occurs after missing 2 scheduled radiological assessments and last assessment prior to missing ≥ 2 scans is not iUPD	Date of last radiological assessment before missing 2 scans	Censor

iPFS = Date of Event or Censor – Date of First Dose +1

Missing 2 scheduled imaging assessments:

Missing 2 scheduled imaging assessments is defined as the gap between two imaging assessments being more than 140 days (2.5 times the scheduled imaging assessment interval (2.5 x 56 days)). Imaging assessments after first iUPD will be excluded from PFS derivation.

Note: Participant cannot be censored at “NE”. If NE is the only previous assessment, then iPFS will be censored at Day 1.

To apply the cut-off date to iPFS is to exclude those tumor assessments after cut-off date and anti-cancer therapy date after cut-off date in the analysis.

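### SAP Table 2 is inconsistent on the iPFS event date when iUPD is followed by death before confirmation, and its literal reading lengthens iPFS

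*SAP*

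**What the plan says.** SAP 5.1.2.5 defines iPFS as time to "death from any cause or radiographic disease progression assessed per iRECIST by investigator assessment, whichever occurs first". It then says that an iUPD is ignored if iSD, iPR or iCR is seen later. It names no other way for an iUPD to be cancelled.

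Table 2 turns this into rows. Four matter here:

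- **Death row (no new therapy):** "No iCPD, but death recorded on eCRF". The event is at the date of death.
- **iUPD-dated row (no new therapy):** "No iCPD nor death and is in one of the following cases". The event is at "First date where iUPD criteria are met". Case b of its list is that "no further response assessments are done (because of participant refusal, protocol non-compliance, or participant death".
- **New-therapy row:** "iUPD before new ACT and is in one of the following cases". It has the same cases a to c, but its heading does not exclude death. The event is at first iUPD.
- **Missed-scan row:** "If last assessment prior to missing ≥ 2 scans is iUPD". The event is at first iUPD, with no exception for death.

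The table states no order of precedence among its rows. SAP 6.4.2.5 summarises iPFS by Kaplan-Meier methods, and SAP 6.1 gives medians with 2-sided 90% confidence intervals.

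**The concern.** Take a participant without new therapy who has iUPD and dies before the confirmatory scan. The headings send this participant to the death row. Case b of the iUPD-dated row describes the same participant, but that row's heading shuts out anyone who has died, so its mention of death can never be used. Either the heading or the case list is wrong.

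The consequence is an odd ordering. A participant who has iUPD and then refuses further scans has an event at iUPD. One who has iUPD and then dies is credited with the extra time up to death. The worse outcome earns the longer iPFS. Early death after iUPD is plausible here: most participants will have exhausted standard therapy, and ECOG status up to 2 is allowed (protocol 5.1).

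**Working it through.** No sample size, power or alpha figure bears on this point. The only number in the iPFS rules is the missed-scan gap, and it reproduces: 2.5 × 56 = 140 days.

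**Inputs**

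- iPFS = event date − first dose date + 1 (below SAP Table 2).
- Scans every 8 weeks, that is 56 days, from C1D1 (protocol 7.1). The first scan is nominally on Day 1 + 56 = Day 57.
- Confirmation of progression 4 to 8 weeks after it is first seen, that is 28 to 56 days (protocol 7.1).

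**Step 1: which date each provision gives.** Test participant: iUPD on Day 57, no later scan, no new therapy, death *g* days after the iUPD scan.

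- Death row, by its heading: date of death.
- iUPD-dated row, by case b: first iUPD. By its heading, the row does not apply.
- Definition (the earlier of progression and death): the iUPD scan comes first.
- Rule for disregarding iUPD: death is not among the outcomes that cancel it, so the iUPD stands.
- New-therapy row, for an otherwise similar participant who started new therapy: first iUPD.
- Missed-scan row: first iUPD. It defines the gap as "the gap between two imaging assessments being more than 140 days (2.5 times the scheduled imaging assessment interval (2.5 x 56 days", so whether a gap that ends in death rather than a scan counts is itself unclear. The companion row, which censors progression or death after two missed scans, is limited to participants whose last scan was not iUPD. This suggests that deaths after iUPD were meant for the iUPD date.

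**Step 2: size for one participant.**

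- Event at iUPD: 57 − 1 + 1 = 57 days, whatever *g* is.
- Event at death: (57 + *g*) − 1 + 1 = 57 + *g* days.
- *g* = 28: 85 days. *g* = 56: 113 days. *g* = 140, the most before the missed-scan row could come into play: 197 days.
- Same iUPD, alive, no further scan: 57 days.

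A participant must be alive to be scanned, so *g* cannot be negative. The death row can therefore lengthen iPFS but never shorten it.

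**Step 3: group illustration, on assumptions only.** The documents give neither the share of progressors who die before confirmation nor the gap. Assume a share *f* of 10% to 30% and a gap uniform over 14 to 56 days, with the upper end set at the confirmation limit. The mean gap is (14 + 56) / 2 = 35 days. The rise in mean iPFS among progressors is *f* × 35:

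- 10%: 3.5 days
- 20%: 7 days
- 30%: 10.5 days

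These are means, whereas the SAP reports a median. First iUPD dates cluster on 8-weekly scan days, so the curve falls in steps. Re-dating a few events may leave the median where it is or move it, depending on where the 50% point falls.

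**The case against.** The strongest reply is that Table 2 does not really give two dates. For a participant without new therapy the two headings are mutually exclusive, so read strictly the date of death applies and the mention of death in case b is redundant. The list a to c is repeated across four Table 2 rows, two of which censor, which looks like carried-over text. This is right as far as it goes. A reader might infer that the result rests on whichever row the programmer happens to choose, and for these two rows the headings do not support that. But the strict reading is the one that lengthens iPFS, and it disagrees with the definition, the rule for disregarding iUPD and the parallel rows.

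A reader might also think that striking the death exclusion from the iUPD-dated row is enough. It is not. That row never says that an iUPD occurred. Without the exclusion, a participant with iSD at the last scan who then dies would satisfy case b and be sent to an iUPD date that does not exist.

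The reply is also right about weight. iPFS is secondary and untested. The study closed early (SAP 5.1.1). Both iPFS and RECIST v1.1 PFS are listed, so affected participants can be found. Table 3 dates documented progression at the scan without waiting for confirmation, so PFS largely avoids the problem.

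**Conclusion.** The inconsistency stands. For iUPD followed by death before confirmation, without new therapy, the headings give the date of death, and everything else in SAP 5.1.2.5 that bears on the case gives the first iUPD date. The direction is certain. For a death inside the confirmation window, the excess is 28 days at its start and 56 days at its end.

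The group effect is not established. The 3.5 to 10.5 days are a mean that rests wholly on an assumed share and gap. A reader might infer a given percentage inflation of median iPFS, but the documents do not supply the inputs for one. Nor do they support any inference that efficacy conclusions are at risk: the stated hypotheses concern iORR (protocol 9.1, SAP 3), which these rules do not touch. The point deserves correction because SAP version 2.0 reduced the number of analyses yet kept iPFS summarised and listed, and in small groups a few re-dated events could matter.

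**What to change.** In SAP Table 2:

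1. Limit the death row to: *no iCPD, death recorded, and no iUPD standing at death (no iUPD, or iUPD followed by iSD, iPR or iCR)*.
2. Re-head the iUPD-dated row: *iUPD not followed by iSD, iPR or iCR, no iCPD, and in one of the cases below*, without the exclusion of death.
3. State the order of precedence among rows, including against the missed-scan row, and say whether a gap that ends in death counts as missed scans.
4. Reconcile the same clash in Table 4 (iDOR), which also excludes death in a heading, names it in case b, and has no row for death.

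Under this rule the test participant has 57 days whatever the date of death. The cost is SAP wording and one programming condition, with no new data. If the database is already locked, state in the CSR which rule was used.

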5.1.2.7 Duration of Response per iRECIST (iDOR)

iDOR is defined as the time from the date of the first response iCR/iPR (whichever is first recorded) to the date of radiographical progression or date of censoring. iDOR will be

calculated only for the subgroup of participants with confirmed response iCR/iPR per iRECIST separately for investigator assessment.

Table 4 iDOR Definition

iDOR		
Situation	Date of Event or Censor	Outcome
Participant did not receive new anti-cancer therapy		
iCPD	First date where iUPD criteria are met	Event
No iCPD nor death and NOT in one of the following cases : a) the participant stops protocol treatment because they were not judged to be clinically stable, b) no further response assessments are done (because of participant refusal, protocol non-compliance, or participant death); c) the next timepoint responses are all iUPD, and iCPD never occurs;	Date of last radiological assessment	Censor
No iCPD nor death and is in one of the following cases : a) the participant stops protocol treatment because they were not judged to be clinically stable, b) no further response assessments are done (because of participant refusal, protocol non-compliance, or participant death); c) the next timepoint responses are all iUPD, and iCPD never occurs;	First date where iUPD criteria are met	Event
Participant received new anti-cancer therapy		
No progression before new ACT	Date of last radiological assessment before start of new ACT	Censor
iCPD before new ACT	First date where iUPD criteria are met	Event
iUPD before new ACT and NOT in one of the following cases : a) the participant stops protocol treatment because they were not judged to be clinically stable, b) no further response assessments are done (because of participant refusal, protocol non-compliance, or participant death); c) the next timepoint responses are all iUPD, and iCPD never occurs;	Date of last radiological assessment before start of new ACT	Censor

iDOR		
Situation	Date of Event or Censor	Outcome
Participant did not receive new anti-cancer therapy		
iUPD before new ACT and is in one of the following cases : a) the participant stops protocol treatment because they were not judged to be clinically stable, b) no further response assessments are done (because of participant refusal, protocol non-compliance, or participant death); c) the next timepoint responses are all iUPD, and iCPD never occurs;	First date where iUPD criteria are met	Event

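### The iPFS and iDOR event row for participants without new therapy does not require an iUPD, so a participant who never progressed can become an event with no date

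*SAP*

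**What the plan says.** SAP section 5.1.2.5 defines iPFS as time from the start of treatment to death or radiographic progression under iRECIST. Table 2 turns this into rows.

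Two rows cover participants with no new therapy who have neither iCPD nor death:

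- "No iCPD nor death and not in one of the following cases": censored at the last scan.
- "No iCPD nor death and is in one of the following cases": an event, dated "First date where iUPD criteria are met".

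The cases are: (a) treatment was stopped because the participant was not judged clinically stable; (b) "no further response assessments are done (because of participant refusal, protocol non-compliance, or participant death"; (c) "next timepoint responses are all iUPD, and iCPD never occurs".

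Table 4 (section 5.1.2.7, iDOR) repeats the pair, with the censoring row opening "No iCPD nor death and NOT in one of the following cases".

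The rows for participants who did receive new therapy are built differently. Their event row opens "iUPD before new ACT and is in one of the following cases", and a separate row, "No progression before new ACT", censors.

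Section 5.1.2.5 also says that an iUPD followed by iSD, iPR or iCR is ignored for iPFS. Section 5.1.2.7 has no such sentence. iPFS is summarized by Kaplan-Meier (section 6.4.2.5) and iDOR is only listed (section 6.4.2.7).

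**The concern.** Within the no-new-therapy block, the two rows are exact complements that split only on cases a to c. Of these, only case c presupposes an iUPD. A participant who never had one can therefore meet case a or b, fall into the event row, and be shut out of the censoring row. The event date that the row then asks for does not exist.

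The rule cannot be programmed as written. The programmer must drop the participant, invent an event date, or override the SAP and censor. Dropping the participant or counting an event lowers the iPFS curve, because it takes away time from people who were progression-free when last seen. The study is open-label and SAP version 2.0 relies on investigator assessment, so this choice should not be left until the data are in view.

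**Working it through.** The SAP gives no figure for this rule beyond the gap definition, which checks: 2.5 × 56 = 140 days. The rest is a row-by-row reading. I applied Table 2 literally to typical participants, then again with an unreset iUPD required before cases a to c can make an event.

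| Participant (no iCPD, no death) | Table 2 as written | With an unreset iUPD required |
|---|---|---|
| iSD, iPR or iCR, refuses scans, no new therapy | Event, no date | Censored at last scan |
| Stops as not clinically stable, never iUPD, no new therapy | Event, no date | Censored at last scan |
| iUPD, then iSD, then refuses scans, no new therapy | Event at an iUPD date the iPFS text ignores | Censored at last scan |
| iSD or iPR, refuses scans, then new therapy | Censored at last scan before it | Unchanged |
| iUPD, then refuses scans, no new therapy | Event at the iUPD date | Unchanged |
| iUPD, all later scans iUPD, no new therapy | Event at the iUPD date | Unchanged |

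Three comparisons inside the SAP show that the first three results are not intended:

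- The iPFS definition needs death or radiographic progression. The participants in the first two lines have neither, and the iUPD in the third is one the text says to disregard.
- The first and fourth lines differ only in whether new therapy was started, yet one is an undated event and the other is censored.
- Table 3 censors a participant with neither RECIST progression nor death, so PFS and iPFS would disagree for someone who progressed under neither criterion.

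**Missed-scan rows.** Both tables contain a row that censors at the last scan when the assessment before two or more missed scans was not iUPD. The note under each table defines this as a gap of more than 140 days between two imaging assessments. A participant who never returns has no second assessment. If the row is nevertheless read to cover that participant, it and the event row give opposite outcomes, and no precedence is stated.

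**Table 4 and the reset.** Take a responder with iUPD on Day 57, iPR first seen on Day 113 and later confirmed, who then refuses scans. Table 4 makes this an event at the first iUPD. Its formula (event date minus first response date plus 1) gives 57 − 113 + 1 = −55 days. Nothing in section 5.1.2.7 says to ignore that iUPD.

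**Size, as illustration only.** Assume exponential iPFS with a median of 150 days, so that 24-week iPFS (168 = 3 × 56 days) is 2^(−168/150) = 0.46. Assume that a fraction q of progression-free participants stops scanning after each scan and is counted as an event. The estimate is then about 0.46 × (1 − q)³:

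- q = 2%: 0.43
- q = 5%: 0.39
- q = 10%: 0.34
- q = 20%: 0.24

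Simulated cohorts of 43 agree closely, and dropping these participants instead gives nearly the same values. With a median of 90 days and q = 10%, 0.27 becomes 0.20. None of these medians or stopping rates comes from the documents.

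**The case against.** The strongest reply is that the intent can be recovered. The date column and case c presuppose an iUPD, and the definition above Table 2 does not allow an event without progression or death. That is right about intent, and a reader should not infer that the plan deliberately counts stable participants who leave as progressed. But intent does not repair the rule, because the complementary row expressly excludes these participants from censoring.

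A second reply is that the missed-scan rows already censor them. This stands in part: it would be wrong to say that no other censoring row could be thought to apply. On their own definition, however, those rows either miss the participant who never returns or conflict with the event row.

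A third reply is that the consequence is small and visible. Much of this stands. iPFS is a secondary, descriptive endpoint, a missing event date is a detectable failure, and RECIST PFS is reported alongside. The illustration above mostly restates its assumed stopping rate. It also uses 43, the planned maximum for a monotherapy expansion cohort, in a study that closed early. Even at 43, the binomial standard error near 0.46 is √(0.46 × 0.54 / 43) = 0.076, more than the loss of about 0.07 at q = 5%. Scanning that ends because the study closes is not refusal or non-compliance, so not every participant without further scans is affected.

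**Conclusion.** The point holds as a wrong derivation rule, most likely a drafting omission, in Tables 2 and 4. A participant without new therapy who never had iUPD and meets case a or b is an event with no date. In Table 2, a reset iUPD supplies a date that the text disregards.

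The direction for iPFS is downward if such participants are dropped or counted as events. There is no bias from this source if the programmer censors them against the table's wording. The size depends on how many there are, which the documents do not say, so none of the illustrative figures should be quoted as an expected bias.

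A reader might also infer that iDOR estimates are distorted. SAP version 2.0 produces no Kaplan-Meier estimate of iDOR, so the effect there is limited to wrong or blank flags and dates in a listing. Primary iORR does not use these rows.

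**What to change.** In both tables:

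1. Event row: an iUPD not followed by iSD, iPR or iCR, with no iCPD and no death, and in one of cases a to c. Event at the first date of that iUPD.
2. Censoring row: all other participants in the block with no iCPD and no death. Censored at the last evaluable radiological assessment. The existing Table 2 row for participants with no evaluable post-baseline imaging stays as it is.
3. State that the iUPD reset rule also applies to iDOR. Check it against the notes under the tables that exclude scans after a first iUPD.
4. Remove participant death from case b in rows that already require no death. Table 4 has no row for a responder without new therapy who dies without iCPD, so say how that participant is handled.
5. State whether the missed-scan rows or the case rows take precedence, and whether the missed-scan rows cover a participant who never returns.

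The cost is two rows in each of two tables plus three short statements, with no new data and no operational change. SAP section 1 places final approval before database hardlock. If that point has passed, the rule actually applied should be recorded in the clinical study report.
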